## 4.2 Exclusion Criteria

1. Subjects with insulin-dependent diabetes:
  - a. Has a history of type 1 diabetes mellitus or a history of ketoacidosis, or subject is assessed by the investigator as possibly having type 1 diabetes mellitus confirmed by a C-peptide  $< 0.7 \text{ ng/mL (0.23 nmol/L)}$ .
  - b. Has a history of other specific types of diabetes (e.g., genetic syndromes, secondary pancreatic diabetes, diabetes due to endocrinopathies, drug- or chemical-induced, and post-organ transplant).
2. Treatment with glucosidase inhibitor, insulin secretagogues (other than sulfonylureas), glucagon-like peptide 1 (GLP-1) agonists within 3 months prior to Visit 1.
3. History of any basal, pre-mix or prandial insulin (greater than 7 days) within 6 months prior to Screening.
4. History of  $> 2$  episodes of severe hypoglycemia within 6 months prior to Screening.
5. History of hypoglycemic unawareness (episodes of severe hypoglycemia with seizure or requiring third party intervention or documented low blood glucose without associated autonomic symptoms).
6. Subjects with the following secondary complications of diabetes:
  - a. Active proliferative retinopathy as confirmed by a dilated ophthalmoscopy/retinal photography examination performed (by a qualified person as per the country legislation) within 6 months prior to Screening.
  - b. Renal dysfunction: estimated creatinine clearance  $< 30 \text{ ml/min}$ .
  - c. History of proliferative retinopathy or severe form of neuropathy or cardiac autonomic neuropathy (CAN).
  - d. Uncontrolled or untreated severe hypertension defined as systolic blood pressure above or equal to 180 mmHg and/or diastolic blood pressure above or equal to 120 mmHg.
  - e. Presence of unstable angina or myocardial infarction within 6 months prior to Screening, Grade 3 or 4 congestive heart failure (CHF) according to the New York Heart Association (NYHA) criteria, valvular heart disease, cardiac arrhythmia requiring treatment, pulmonary hypertension, cardiac surgery, history/occurrence of coronary angioplasty and/or stroke or transient ischemic attack (TIA) within 6 months prior to Screening.
7. Subjects with psychiatric disorders which, per investigator judgment, may have impact on the safety of the subject or interfere with subject's participation or compliance in the study.
8. Subjects who needed (in the last 12 months) or may require systemic (oral, intravenous, intramuscular) glucocorticoid therapy for more than 2 weeks during the study period.
9. Laboratory abnormalities at Screening including:

- a. C-peptide < 0.7 ng/mL (0.23 nmol/L).
- b. Abnormal serum thyrotropin (TSH) levels below the lower limit of normal or > 1.5X the upper limit of normal.
- c. Elevated liver enzymes (alanine transaminase (ALT), alanine aminotransferase (AST), alkaline phosphatase) > 2X the upper limit of normal.
- d. Very high triglyceride levels (> 600 mg/dL); a single repeat test is allowable.
- e. Any relevant abnormality that would interfere with the efficacy or the safety assessments during study treatment administration.

10. Positive history of active liver disease (other than non-alcoholic hepatic steatosis), including chronic hepatitis B or C, primary biliary cirrhosis, or active symptomatic gallbladder disease.

11. Positive history of HIV.

12. Use of the following medications:

- a. History of any basal, pre-mix or prandial insulin (greater than 7 days) within 6 months prior to Screening.
- b. Administration of thyroid preparations or thyroxine (except in subjects on stable replacement therapy) within 6 weeks prior to Screening.
- c. Administration of systemic long-acting corticosteroids within two months or prolonged use (more than one week) of other systemic corticosteroids or inhaled corticosteroids (if daily dosage is > 1,000 µg equivalent beclomethasone) within 30 days prior to Screening. Intra-articular and/or topical corticosteroids are not considered systemic.
- d. Use of medications known to modify glucose metabolism or to decrease the ability to recover from hypoglycemia such as oral, parenteral, and inhaled steroids (as discussed above), and immunosuppressive or immunomodulating agents.

13. Known allergy to soy.

14. Subject is on a weight loss program and is not in the maintenance phase, or subject has started weight loss medication (e.g., orlistat or liraglutide), within 8 weeks prior to Screening.

15. Subject has had bariatric surgery.

16. Subject is pregnant or breast-feeding.

17. Subject is a user of recreational or illicit drugs or has had a recent history (within 1 year of Screening) of drug or alcohol abuse or dependence. (Note: Alcohol abuse includes heavy alcohol intake as defined by > 3 drinks per day or > 14 drinks per week, or binge drinking) at Screening. Occasional intermittent use of cannabinoid products will be allowed provided that no cannabinoid products have been used during the 1 week prior to each visit.

18. Subjects is smoking more than 10 cigarettes per day.

19. One or more contraindications to metformin as per local label.

20. History of gastrointestinal disorders (e.g. hypochlorhydria) with the potential to interfere with drug absorption.

21. At the Principal Investigator's discretion, any condition or other factor that is deemed unsuitable for subject enrollment into the study.

### 4.3 Subject and Trial Discontinuation

Subjects may choose to withdraw from this study at any time for any reason without penalty of jeopardizing their health care or loss of benefits to which the subject is otherwise entitled.

Within the provisions of informed consent and good clinical judgment with respect to safety, every attempt will be made to have subjects complete the study. Reasons for subject discontinuation include, but are not limited to the following:

1. Subject experiences an AE that in the judgement of the Investigator poses a significant risk to the subject for continued participation in the study.
2. Subject uses a prohibited medication (listed in [Section 5.6](#)) that in the judgment of the Investigator poses a significant risk to the subject for continued participation in the study or that will interfere with the interpretation of the results of the study.
3. Subject becomes pregnant.
4. Significant protocol violation or noncompliance on the part of the subject or the Investigator.
5. Intercurrent illness that requires treatment that is not consistent with the protocol requirements, or intercurrent illness or the associated treatment that in the judgment of the Investigator poses a significant risk to the subject for continued participation in the study.
6. Episodes of hypoglycemia not responsive to changes in diet or dose regimen ([Section 7.4.3](#))
7. Subject meets one of the exclusion criteria during the study
8. Subject wishes to withdraw for any reason.
9. Sponsor elects to end the study, or the Investigational Site elects to end the study at their site.
10. Any other reason that in the judgment of the Investigator poses unacceptable risk to the subject.

Subjects who withdraw from the study may be replaced at the discretion of the investigator and will be discussed on a case-by-case basis.

Except in cases of emergency, the Investigator should consult with the Sponsor and the Medical Monitor before removing the subject from the study. In some circumstances, it may be necessary to temporarily interrupt treatment as a result of AEs that may have an unclear relationship to study treatment. The investigator should obtain approval from the Sponsor and Medical Monitor before restarting study treatments that were temporarily discontinued for an AE.

In the event that a subject discontinues the study prior to completion, the date the subject is withdrawn and the reason for discontinuation will be recorded in the source documents and eCRF. Although a subject will not be obliged to give his/her reason for withdrawing prematurely, the investigator will make a reasonable effort to obtain the reason while fully respecting the subject's rights.

All subjects who are randomized and treated (i.e., received any amount of study treatment) will be included in the safety analyses. Thus, every effort will be made to contact any subject who fails to attend any follow-up appointments/contacts, in order to ensure that he/she is in satisfactory health. If a subject withdraws from the study as a result of meeting discontinuation criteria after the start of study treatment administration, reasonable efforts should be made to have the subject return for the

early withdrawal evaluations ([Section 3.6](#)). Any subject withdrawn due to a suspected study treatment-related AE should be followed until resolution or stabilization of the event.

If a subject becomes pregnant, study treatment will be discontinued immediately. The subject will be followed until delivery or other termination of pregnancy for outcome.

The Sponsor has the right to terminate this study, and the Investigator/Investigational Site has the right to close the site, at any time, although this should occur only after consultation between involved parties. The Investigator will notify the IRB in writing of a premature termination of a study or closure of Investigational Site, and will send a copy of the notification to the Sponsor.

Events that may trigger premature termination of a study or closure of an Investigational Site include, but are not limited to, a new toxicity finding, a request to discontinue the trial from a regulatory authority, non-compliance with the protocol, GCP violations, slow recruitment/low enrollment, or change in development plans for the study treatment.

If either of the criteria listed below is met, enrollment of new subjects and dosing of ongoing subjects will be temporarily stopped. The Investigator, Sponsor, and the Medical Monitor will discuss whether a lower dose or any additional treatment guidelines should be implemented, or if the trial should be permanently stopped. Any proposed changes to the protocol to address such findings will be submitted for review and approval by the IRB and FDA prior to re-starting the trial.

1. A death within 30 days after study treatment administration where there is a reasonable possibility that the drug caused the event;
2. Two Grade 4 AEs where there is a reasonable possibility that the study treatment caused the events.

## 5 STUDY TREATMENT

### 5.1 Description of Investigational Drug

Active:

Code name: ORMD-0801

Dosage form: 1 soft gel capsule per dose to be administered twice daily

Strength: 8 mg insulin per capsule

Description: Soft gel capsule [SBTI, disodium EDTA, fish oil, aerosol, and Tween 80], Recombinant Human Insulin

Placebo control:

Fish oil in capsules, identical in appearance to ORMD-0801, administered twice daily

#### 5.1.1 Packaging and Labeling

All study medication will be shipped in bulk. The unblinded investigational site pharmacist or designee will be responsible for dispensing the appropriate study treatment based on the

randomization schedule. Study medication will be distributed at each visit sufficient to cover the time between visits. Subjects will receive one bottle each at Visit 1 and Visit 2 to self-administer doses at home. Subjects will be dosed in-clinic from a new bottle at Visit 3.

Study medication will be dispensed to the site with instructions for when treatment can be administered. Unused study medication will be returned or destroyed according to instructions provided by Oramed Ltd.

The treatment packages will be labeled with the following information:

- Study number
- Bottle ID
- Dosage Form/Content
- Directions for use, including route of administration
- Number of capsules in package
- Storage conditions
- Instructions to “keep out of reach of children”
- Caution: New Drug – Limited by Federal (or United States) law to investigational use.
- Name of Sponsor

A label with the identical information will be made available for drug accountability purposes.

### 5.1.2 Storage and Handling

All study treatment must be kept in an appropriate, secure area to prevent unauthorized access. The study treatment is to be shipped under refrigerated conditions and stored at controlled temperature (36 to 46°F; 2 to 8°C). Excessive humidity should be avoided. Storage conditions will be monitored and appropriate monitoring logs maintained as source data. Deviations from the established temperature, as well as the occurrence of excessive humidity, should be documented, and the Sponsor should be notified. Study treatment should be handled using proper procedures as defined by investigational site standard operating procedures (SOPs) for Investigational Drugs. IMP will be returned or destroyed according to instructions provided by Oramed Ltd. Drug destruction procedures and documentation must be retained at the site.

## 5.2 Randomization

This is a randomized, double blind, parallel study. Approximately 40 subjects with T2D will be randomized to one of two treatment groups.

Integrium, LLC will generate and implement the randomization procedures for this trial. A computer-generated randomization schedule will be used for assigning the treatment groups. The Investigational Site pharmacist will follow this randomization schedule to dispense the appropriate study treatment.

## **5.3 Study Treatment Administration**

### **5.3.1.1 Double-Blind Treatment Administration**

All subjects will receive double-blind placebo or ORMD-0801 (8 mg insulin) twice a day, once in the morning and once in the evening, according to their randomization schedule from Visit 1 (Day 0) to Visit 3 (Day 28). Subjects will take one capsule (active or placebo), 45 minutes ( $\pm$  15 minutes) before breakfast and no later than 10 AM each morning, and one capsule at 8 PM ( $\pm$  120 minutes at Visits 1-2 and  $\pm$  60 minutes at Visit 3) each night, and no sooner than 1 hour after dinner.

## **5.4 Measuring Subject Compliance**

Dosing compliance will be assessed through a count of unused study medication at each clinic visit.

## **5.5 Drug Accountability**

In accordance with current GCP, the Investigational Site will account for all study treatment supplies. Details of receipt, storage, administration, and return or destruction will be recorded in the Investigational Drug accountability record according to the SOP of the Investigational Site. Copies of the Investigational Drug accountability record will be provided to the Sponsor.

Study treatment will only be dispensed to subjects enrolled in this protocol, and only as directed by this protocol. Administration of study treatment will be accurately recorded in each subject's source documents and in the eCRF.

## **5.6 Concomitant Medications and Supplements**

All medications and supplements (other than study treatment) taken by the subject from Visit 1 through Visit 3 will be considered "concomitant" medications and supplements. Medications and supplements taken prior to Visit 1 that are no longer being taken at the time of Visit 1 will be considered "prior" medications and supplements.

All medications and supplements taken within 30 days prior to the first dose of study treatment and concomitant medications and supplements taken during the course of the study will be recorded in the subject's source documentation and in the eCRF.

If a subject requires the use of any of the prohibited medications and supplements listed below, the investigator will contact the Sponsor and the Medical Monitor to discuss the subject's continued participation in the study. In the event of an emergency, subjects will be treated at the discretion of the investigator according to acceptable community standards of medical care.

The following are prohibited medications:

1. Any Investigational Drug other than ORMD-0801 (or placebo) within 30 days prior to Visit 1 through Visit 3;
2. Any anti-diabetic drugs (except for those allowable by the inclusion criteria) including insulin, GLP-1 analogue,  $\alpha$ -glucosidase inhibitors, glinides, and pramlintide unless required for rescue;
3. Thyroid preparations or thyroxine (except in subjects on stable replacement therapy);

4. Systemic long-acting corticosteroids or other systemic corticosteroids or inhaled corticosteroids (if daily dosage is > 1,000 µg equivalent beclomethasone). Intra-articular and/or topical corticosteroids are not considered systemic.
5. Medications known to modify glucose metabolism or to decrease the ability to recover from hypoglycemia such as oral, parenteral, and inhaled steroids, and immunosuppressive or immunomodulating agents.

If the subject initiates prohibited drug therapy, or if the investigator determines that use of a prohibited therapy is in the best interest of the subject's health and well-being, the investigator and sponsor will jointly decide to continue or discontinue study treatment for the subject.

Medications and supplements should be recorded according to the generic name when possible. The use of concomitant medications and supplements should be limited to those that are medically necessary. Any medication or supplement used should have an indication recorded, and for concomitant medications and supplements, this indication must be represented as either for the treatment of an AE, for the management of a pre-existing condition, or for prophylaxis.

Dosage increases for any concomitant medication or supplement should be noted and the reason for the dosage increase recorded as an AE (assumes worsening condition). The side effects of concomitant medications will be recorded as AEs.

Any subject whose condition becomes disqualifying during the course of the study may be treated for that condition. If the condition is suspected during Screening (Visit 0), the subject should not be enrolled. Treatment of the condition should be instituted according to the Investigator's/attending physician's judgment.

Medications that have no treatment intent but rather are part of supportive routine care such as local anesthetics, intravenous solutions to maintain fluid balance and keep access open, medications used for prophylaxis, and narcotics for postsurgical pain must also be recorded in the subject's medical record and eCRF.

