#### **3.3.2 Visit 2 (Week 2, Day 14)**

Subjects will report to the clinic in morning following a 10-hour fast. At Visit 2, the following procedures will be performed:

- Review of prior and current medications and supplements;
- Measurement of vital signs (SBP/DBP and heart rate);
- Measurement of weight;
- Breathalyzer;
- Study medication will be collected, and compliance will be reviewed;
- Study medication will be dispensed;
- Blood sample will be collected to measure HbA1c;
- AEs/SAEs assessment;
- Remind subjects to arrive fasting for Visit 3 in 2 weeks.

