## 4 STUDY SUBJECT SELECTION

### 4.1 Inclusion Criteria

1. Male and female subjects aged, 18 - 70 years.
2. Established diagnosis of T2DM for at least 6 months prior to Screening, with HbA1c  $\geq 7.5\%$ . and  $\leq 11\%$ .
3. Stable dose of metformin (at least 1500 mg or maximal tolerated dose) for a period of at least 3 months prior to Screening.
4. Taking metformin only or metformin in addition to no more than two of the following: DPP-4, SGLT-2, or TZD.
5. Body mass index (BMI) of up to  $35 \text{ kg/m}^2$  at Screening and stable weight, with no more than 5 kg gain or loss in the 3 months prior to Screening.
6. Renal function – eGFR  $> 30 \text{ ml/min/1.73 m}^2$ .
7. Females of childbearing potential must have a negative serum pregnancy test result at Screening.
  - a. Females who are not of childbearing potential are defined as:
    - i. Postmenopausal (defined as at least 12 months with no menses in women  $\geq 45$  years of age);
    - ii. Has had a hysterectomy and/or bilateral oophorectomy, bilateral salpingectomy, or bilateral tubal ligation/occlusion at least 6 weeks prior to screening; OR
    - iii. Has a congenital or acquired condition that prevents childbearing.
  - b. Females of childbearing potential agree to avoid becoming pregnant while receiving study treatment and for 14 days after the last dose of study treatment by complying with one of the following:
    - i. Practice abstinence† from heterosexual activity; OR
    - ii. Use (or have her partner use) acceptable contraception during heterosexual activity. Acceptable methods of contraception are‡:
      1. Single method (one of the following is acceptable):
        - a. Non-hormonal intrauterine device (IUD);
        - b. vasectomy of a female subject's male partner.
      2. Combination method (requires use of two of the following):
        - a. diaphragm with spermicide (cannot be used in conjunction with cervical cap/spermicide);
        - b. cervical cap with spermicide (nulliparous women only);
        - c. contraceptive sponge (nulliparous women only);
        - d. male condom or female condom (cannot be used together).

†Abstinence (relative to heterosexual activity) can be used as the sole method of contraception if it is consistently employed as the subject's preferred and usual lifestyle and if considered acceptable

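### Only metformin must be at a stable dose, and only up to Screening; add-on glucose-lowering drugs have no stability condition, and no background dose is fixed through the single EGP measurement

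*Combined protocol and SAP*

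**What the plan says.** Section 4.1, criterion 3, sets the only stability condition on a glucose-lowering drug: "Stable dose of metformin (at least 1500 mg or maximal tolerated dose) for a period of at least 3 months prior to Screening". It covers metformin alone and ends at Screening. Criterion 4 describes the permitted regimen as "Taking metformin only or metformin in addition to no more than two of the following: DPP-4, SGLT-2, or TZD", with no dose or duration attached to the add-ons. The synopsis repeats both criteria.

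For the period on study, section 5.6 item 2 prohibits "Any anti-diabetic drugs (except for those allowable by the inclusion criteria". The same item ends its list with "glinides, and pramlintide unless required for rescue", and no rescue threshold is given there. Item 3, by contrast, writes a stability condition into its exception: "Thyroid preparations or thyroxine (except in subjects on stable replacement therapy". Later in 5.6, dose increases are dealt with by recording them: "Dosage increases for any concomitant medication or supplement should be noted and the reason for the dosage increase recorded as an AE".

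The primary endpoint is EGP AUC(0-16) from one infusion after 28 days. Section 8.3 compares it by analysis of variance with treatment as the only term. Section 5.2 randomises about 40 subjects and mentions no stratification.

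**The concern.** The add-on classes act on glucose, and the trial's endpoint is glucose production. A subject who started or changed an add-on shortly before entry, or whose metformin or add-on is changed during treatment, contributes an EGP value that partly reflects that change. With one measurement, no baseline and no covariate, neither the design nor the primary model can take this variation out, so control has to come from the eligibility and conduct rules. Those rules cover metformin before Screening and nothing after it.

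Two effects need to be kept apart. A change before randomisation cannot depend on the arm, so it only adds between-subject variance. A change after randomisation can be prompted by glucose, which treatment may influence, so its frequency could differ between arms and bias the difference. The second effect has limited room: treatment lasts four weeks, and the only scheduled glycaemic result between the first dose and Day 28 is at Visit 2 ("Blood sample will be collected to measure HbA1c"). Other prompts would be unscheduled readings or symptoms.

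**Working it through.** **The rules side by side**

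| Drug | Before Screening | Screening to end of infusion |
|---|---|---|
| Metformin | Stable for at least 3 months (4.1, criterion 3) | Permitted; no fixed-dose rule |
| DPP-4, SGLT-2, TZD | No condition (4.1, criterion 4) | Permitted; no fixed-dose rule |
| Thyroid replacement | Stable replacement excepted (4.2, criterion 12b) | Stable replacement excepted (5.6, item 3) |

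Nothing in sections 3.2, 4.1, 4.2, 4.3, 5.6 or 8 fills the gaps in the first two rows. Section 8 defers detail to a statistical analysis plan, but an analysis plan cannot make doses stable after the event.

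**Size, for illustration**

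The plan has no figure to reproduce; section 8.2 states that the sample size had no statistical basis. The inputs below are therefore assumptions, except the total of about 40:

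- 20 subjects per arm (equal split assumed), working in units of the between-subject SD of AUC(0-16).
- g = shift in AUC for a subject with a changed background dose, compared with the same subject had the dose been stable: 0.3, 0.5 or 1.0 SD.
- p = share of subjects with a recent change before randomisation: 10% or 20%.
- x = excess share of changed subjects in one arm after randomisation: 1/20 = 0.05 or 2/20 = 0.10.

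Standard error of the difference = √(2/20) = 0.316 SD.

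*Before randomisation (noise).* Variance factor V = 1 + p(1 − p)g². Equivalent subjects lost = 40 − 40/V. Example: p = 0.10, g = 0.5 gives V = 1 + 0.09 × 0.25 = 1.0225, and 40 − 40/1.0225 = 0.88.

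| p | g = 0.3 | g = 0.5 | g = 1.0 |
|---|---|---|---|
| 10% | 0.32 | 0.88 | 3.30 |
| 20% | 0.57 | 1.54 | 5.52 |

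*After randomisation (possible bias).* Bias = x × g; the brackets give bias ÷ 0.316.

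| Excess in one arm | g = 0.3 | g = 0.5 | g = 1.0 |
|---|---|---|---|
| 1 of 20 | 0.015 SD (4.7%) | 0.025 SD (7.9%) | 0.05 SD (15.8%) |
| 2 of 20 | 0.03 SD (9.5%) | 0.05 SD (15.8%) | 0.10 SD (31.6%) |

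Either sign is possible.

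*Time to settle.* Screening is at Day −21 to −7 and the infusion starts on Day 28. A change made just before Screening therefore has 28 + 7 = 35 to 28 + 21 = 49 days, that is 5 to 7 weeks, before EGP is measured. For such a subject the larger values of g are the less plausible ones.

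**The case against.** The strongest reply is that a single late measurement has little need of pre-entry stability. Stability before baseline mainly protects change-from-baseline endpoints. Here what matters is the drug the subject is on at Day 28, and a change made just before Screening has had at least five weeks to settle. The permitted mix of one to three background drugs may vary EGP more than recent changes do, and a stability rule leaves that mix alone. This stands, and it keeps the pre-entry effect small.

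The plan also has softer controls. Subjects are told to keep other medication to a minimum (3.2). Use is limited to medical need, and needing a prohibited drug triggers contact with the sponsor and Medical Monitor and a joint decision on continuing (5.6). Prohibited medication that would interfere with interpretation can lead to discontinuation (4.3). Medications are reviewed at each visit and listed by subject (8.5.7), so changes would be visible. These narrow the gap, but none fixes a dose, and the provisions on prohibited drugs do not reach the allowed classes.

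Three stronger readings are not supported:

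- A reader might infer that 5.6 gives sites freedom to start or titrate an allowed class. Criterion 4 describes what subjects are taking at entry, so the exception more naturally means continuing that regimen. The wording does not settle the matter, and that is as far as the point goes.
- A reader might treat chance imbalance in recently changed subjects as a further problem on top of the noise. It is the same sampling variation, already in the ANOVA standard error, and does not bias the test.
- A reader might cite exclusion 2 ("glucagon-like peptide 1 (GLP-1) agonists within 3 months prior to Visit 1") as a stability rule the add-ons lack. It is a washout of disallowed drugs. The fair comparisons are metformin and thyroid replacement.

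**Conclusion.** The gap is real and the effect is probably modest. Add-on glucose-lowering drugs carry no stability condition at entry, and no background glucose-lowering dose, metformin included, is required to stay fixed until the infusion ends.

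Under the assumed shares and shifts, pre-randomisation changes cost the equivalent of 0.3 to 5.5 of 40 subjects in precision, with the upper figure needing a full 1 SD shift in a fifth of subjects. An excess of one or two changed subjects in one arm after randomisation would bias the difference by 0.015 to 0.10 SD. The documents give no rate of change, effect size or direction, so these figures indicate scale only.

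It would be tempting to conclude that the primary comparison is compromised. The documents do not support that: randomisation protects against systematic difference from earlier changes, and four weeks with one scheduled glycaemic result leaves little room for later ones. The change is worth making because it is cheap and cannot be made retrospectively.

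**What to change.** In inclusion criterion 4, after the add-on classes, add:

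> each at a stable dose for at least 3 months prior to Screening.

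In section 5.6, add:

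> Doses of metformin and any allowed add-on stay unchanged, and no allowed class is started, from Screening to the end of the infusion, except for safety: hyperglycemia confirmed > 300 mg/dL or with persistent symptoms (7.4.4), hypoglycemia (7.4.3), intolerance, an adverse event, a new contraindication, or emergency care at the investigator's discretion. Record drug, dose, date and reason.

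Report these changes by arm in one table. The list of exceptions is deliberately broad: a rule limited to glucose thresholds would stop an investigator from withdrawing a drug for intolerance or falling renal function.

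This removes recent add-on changes before Screening and discretionary changes on study. It does not remove differences caused by the safety changes themselves; the table makes those visible. How rescued subjects enter the section 8.3 analysis is a separate question and need not be settled for this fix.

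The cost is a clause, a short paragraph and a table. Candidates with a recent add-on change must wait or are screened out, so enrolment slows somewhat. Background doses are held for about 5 to 7 weeks (1 to 3 weeks of screening plus 4 of treatment).
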